### 5.6.2 Key Efficacy Endpoint Carryover Effect Estimation

If the key efficacy endpoint analysis shows a statistically significant treatment by period interaction ( $p$ -value  $< 0.05$ ), modified key efficacy analyses will be performed to adjust for potential first-order carryover effects on the ESS score. For these analyses, the treatment of the previous treatment period will be assigned to each observation. The treatment by period interaction in the original efficacy model will not be included.

The treatment effects at end-of-treatment visits V1B, V2B and V3B will be estimated using a mixed linear regression model with the fixed effects of treatment, period, sequence, and residual treatment, baseline score as a covariate, and the random effect of subject nested within sequence. The carryover effect estimation will be performed using the following SAS code:

```
PROC MIXED DATA=<Dataset> METHOD=REML;
  CLASS <Subject> <Treatment> <Period> <Sequence> <LagTreatment>;
  MODEL <Change from Baseline> = <Treatment> <Period> <Sequence>
    <Baseline> <LagTreatment>
    / DDFM = KENROG;
  RANDOM int / SUBJECT=<Subject>(<Sequence>);
  LSMEANS <Treatment> / PDIFF CL;
RUN;
```

The following tables will be presented:

Table 15.3.2.3.1 Analysis of Epworth Sleepiness Scale Score Adjusted for Carryover – Full Analysis

Table 15.3.2.3.2 Analysis of Epworth Sleepiness Scale Score Adjusted for Carryover – Per Protocol

Estimates of each modelled effect will be displayed with standard errors, t-values and p-values. Contrast estimates will be displayed for the difference between each pair of direct treatment effects.

### 5.6.3 ESS Responder Rate

The Epworth Sleepiness Scale (ESS) responder rate is defined as the proportion of subjects with a relative ESS score change from baseline of at least -25% after each treatment period.

The treatment differences in the ESS responder rate will be assessed using a generalised linear mixed regression model (GLMM) with the fixed effects of treatment, period, treatment by period interaction, sequence, and baseline score, and subject nested within sequence as a random effect. The logit link function will be used to model the binary response data. The model will be estimated using the default RSPL method. Degrees of freedom for the fixed effects will be estimated using the Kenward-Roger approximation.

The following SAS code will be used in GLMM estimation:

```
PROC GLIMMIX DATA=<Dataset> METHOD=RSPL;
  CLASS <Subject> <Treatment> <Period> <Sequence>;
  MODEL <Responder Status> = <Treatment> | <Period>
                                <Sequence> <Baseline>
                                / DIST=BINARY LINK=LOGIT DDFM = KENROG;
  RANDOM int / SUBJECT=<Subject>(<Sequence>);
  LSMEANS <Treatment> / PDIFF ODDS RATIO ILINK CL;
RUN;
```

The treatment least-squares means of the log-odds will be reported as well as their standard errors and 95% confidence intervals. Also, the odds ratios between each treatment will be displayed with 95% confidence intervals.

In case of model non-convergence, the treatment by period interaction will be removed from the model. If the simplified model fails to converge, the difference in response rate between treatments will be evaluated using an exact McNemar's test. Response at endpoint will be compared between each treatment at the two-sided 5% level.

McNemar's test will be performed using the following SAS code:

```
PROC FREQ DATA=<Dataset>;
  TABLES <Treatment 1 Response> * <Treatment 2 Response>;
  EXACT MCNEM;
RUN;
```

If a statistically significant ( $p$ -value  $< 0.05$ ) treatment by period interaction is found in the analysis of the ESS responder rate, an additional analysis will be performed using only data collected during the first treatment period. If the full GLMM specification was not used due to model non-convergence, this additional analysis will be performed in case of a statistically significant treatment by period interaction in the key efficacy model (Section 5.6.1).

Model-based analysis of first-period data will be based on a generalised linear model (GLM) with the fixed effect of treatment and baseline as a covariate. The following SAS code will be used:

```
PROC GLIMMIX DATA=<Dataset>;
  CLASS <Treatment>;
  MODEL <Responder Status> = <Treatment> <Baseline>
                                / DIST=BINARY LINK=LOGIT;
  LSMEANS <Treatment> / PDIFF CL;
RUN;
```

The following table and listing will be presented:

Table 15.3.3.1.1.S Summary of Epworth Sleepiness Scale Responder Rate – Full Analysis

Table 15.3.3.1.2.S Summary of Epworth Sleepiness Scale Responder Rate – Per Protocol

Table 15.3.3.2.1.T Summary of Epworth Sleepiness Scale Responder Rate – Full Analysis

Table 15.3.3.2.2.T Summary of Epworth Sleepiness Scale Responder Rate – Per Protocol

Epworth sleepiness scale responder rate at each post-baseline visit will be summarised using default frequency tabulations. Percentage will be based on number of subjects with data available at each timepoint.

Table 15.3.4.1.1 Analysis of Epworth Sleepiness Scale Responder Rate – Full Analysis

Table 15.3.4.1.2 Analysis of Epworth Sleepiness Scale Responder Rate – Per Protocol

Table 15.3.4.2.1 Analysis of Epworth Sleepiness Scale Responder Rate (First Period) – Full Analysis

Table 15.3.4.2.2 Analysis of Epworth Sleepiness Scale Responder Rate (First Period) – Per Protocol

Estimates of each modelled effect will be displayed with standard errors, t-values and p-value. Log-odds contrast estimates will be displayed for the difference between each pair of treatments.

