1.3. Rationale for Trial Design and Dose Selection

1.3.1. Trial design

This proof-of-concept, phase IIa trial with THN102 should collect a sufficient body of information to assess the safety and efficacy profile of THN102 versus placebo in Parkinson's disease subjects suffering from excessive daytime sleepiness. The sample size required for a crossover design is approximately one third of the size required in a parallel trial. To use a cross-over option is thus a viable alternative design, with a sample size of about 60 subjects in this condition. In addition, a direct comparison between THN102 doses can be performed in the same subject. The selected trial design for this pilot proof-of-concept phase IIa trial is consequently a randomised, placebo-controlled, 3-way cross-over trial design comparing two dose levels of THN102 to placebo and followed by a washout period of 1-2 weeks. It was perceived as essential to take advantage of the cross-over design for exploring two doses of THN102 and comparing their impact on safety, ESS and other efficacy endpoints. The treatment duration of 2 weeks per period appears sufficient to observe therapeutic activity as the steady state will be reached after about 3 days of drug intake. Each treatment period is followed by a one-week washout period, which can be extended up to two weeks. In addition to the key efficacy endpoint, ESS, other efficacy endpoints have been selected, such as cognitive assessments including PVT and MoCA before and after each treatment period.

A difference of 25% in ESS is considered clinically relevant. [26] Therefore responder rates will be analysed, with responders being defined as subjects with at least 25% improvement from baseline.

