6. MDS-UPDRS
7. QUIP-RS

8.1.2. Efficacy variables

Key Efficacy Endpoint

8. Mean ESS score change from baseline at the end of each treatment period

Secondary Efficacy Endpoints

9. ESS score responder rate, defined as the proportion of patients with at least 25% ESS improvement from baseline, at the end of each treatment period
10. Absence of residual somnolence, i.e. ESS < 11 at the end of each treatment period
11. Psychomotor Vigilance Test (PVT) variables change from baseline at the end of each treatment period
12. MoCA score change from baseline at the end of each treatment period
13. Actimetry change (inactivity) from baseline at the end of each treatment period
14. Number and duration of diurnal involuntary sleep attacks (subject diaries) change from baseline at the end of each treatment period
15. Episodes of somnolence (subject diaries) change from baseline at the end of each treatment period

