#### 2.2.3 Secondary Efficacy Endpoints

The secondary efficacy endpoints of this trial are

9. ESS score responder rate, defined as the proportion of subjects with at least 25% ESS improvement from baseline, at the end of each treatment period
10. Absence of residual somnolence, i.e. ESS < 11 at the end of each treatment period
11. Psychomotor Vigilance Test (PVT) variables change from baseline at the end of each treatment period
12. MoCA score change from baseline at the end of each treatment period
13. Actimetry change (inactivity) from baseline at the end of each treatment period
14. Number and duration of diurnal involuntary sleep attacks (subject diaries) change from baseline at the end of each treatment period
15. Episodes of somnolence (subject diaries) change from baseline at the end of each treatment period

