### Endpoint value

The endpoint value for a variable is defined as the last non-missing value collected during any end-of-treatment visit (V1B, V2B, or V3B).

For diary data, the endpoint value will be the value standardized as described in Section 5.6.8 over any treatment period corresponding to a given treatment.

**Absolute change from baseline** will be calculated as

$$\text{Absolute Change from Baseline at Visit } X = \text{Value at Visit } X - \text{Baseline Value}$$

**Relative change from baseline (%)** will be calculated as

$$\text{Relative Change from Baseline at Visit } X = \frac{\text{Value at Visit } X - \text{Baseline Value}}{\text{Baseline Value}} \times 100$$

Note: Subjects with a baseline value of '0' will be excluded from the calculation of relative change.

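### The ESS responder rule in SAP 5.6.3 is mis-signed against the SAP's own change formula, and the GLIMMIX code for 5.6.3 and 5.6.4 does not say which outcome level is modelled

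*SAP*

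**What the plan says.** **Definition.** SAP 5.6.3 gives the responder rate as "the proportion of subjects with a relative ESS score change from baseline of at least -25% after each treatment period". The same endpoint is worded as an improvement everywhere else: SAP 2.2.3 has "the proportion of subjects with at least 25% ESS improvement from baseline", Protocol 8.1.2 has "the proportion of patients with at least 25% ESS improvement from baseline", and Protocol 1.3.1 explains the threshold, "with responders being defined as subjects with at least 25% improvement from baseline". SAP 4.7 (Endpoint value) sets the sign convention: the visit value minus the baseline value, divided by the baseline value, times 100. SAP section 7, which lists departures from the protocol, does not mention the responder definition.

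**Model code.** The mixed logistic model in SAP 5.6.3 is coded "MODEL <Responder Status> = <Treatment> | <Period>", followed by sequence and baseline, with a binary distribution and logit link. The first-period fallback is coded "MODEL <Responder Status> = <Treatment> <Baseline>", with the same distribution and link. Neither call names the event level, and the SAP text does not say how the status variable is coded. SAP 5.6.4 applies the methods of 5.6.3 to absence of residual somnolence, defined as ESS below 11.

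**The concern.** There are two separate gaps, and both concern direction.

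1. ESS falls when sleepiness improves, so improvement is negative on the SAP 4.7 scale. On that scale a change of at least -25% is a change of -25% or anything above it: small improvement, no change, or worsening. SAP 5.6.3 is the analysis-level definition and the only one written on the signed scale. A programmer who codes from it would invert the status in Tables 15.3.3.x, and no choice made in the model could correct those tables.

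2. A binary logistic model describes one of the two levels. If the plan names neither the level nor the coding, the direction of every log-odds, odds ratio and back-transformed probability depends on an unstated coding and a software default. This matters most in 5.6.4, where the endpoint definition is clear and nothing could offset a wrong event level. It also matters in the first-period code, which requests only differences and confidence limits, with no odds ratios or back-transformed probabilities. The sign of the log-odds contrast is then the main cue to direction.

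**Working it through.** The plan states no responder rate, odds ratio or responder sample size, so there is no figure of its own to reproduce here. The 82% power in SAP 2.6 concerns the key endpoint and does not enter.

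**Step 1. Literal against intended rule.** Inputs: baseline ESS of at least 14 (Protocol 4.2, criterion 6, re-checked at VR); ESS an integer from 0 to 24 (SAP 5.6.1); relative change = (value - baseline)/baseline × 100 (SAP 4.7).

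| Baseline to end | Relative change | Intended (≤ -25%) | Literal (≥ -25%) |
|---|---|---|---|
| 16 to 8 | -50% | responder | not |
| 16 to 12 | -25% | responder | responder |
| 16 to 13 | -18.75% | not | responder |
| 16 to 16 | 0% | not | responder |
| 16 to 20 | +25% | not | responder |

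There are 11 baselines (14 to 24) × 25 end scores (0 to 24) = 275 pairs. The intended rule selects 164 and the literal rule 114. They share 3 (16 to 12, 20 to 15, 24 to 18), and no pair falls outside both: 164 + 114 - 3 = 275. The two rules are therefore complements apart from ties at exactly -25%. These are counts of possible score pairs, not expected frequencies.

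**Step 2. Effect of the modelled level.** Since logit(1 - p) = -logit(p), modelling the other level changes the sign of every coefficient. The odds ratio becomes its reciprocal, and |z| and the two-sided p-value stay the same. For assumed response rates of 30% and 50%, the odds ratio is (0.5/0.5)/(0.3/0.7) = 2.33; with the other level modelled it is 1/2.33 = 0.43.

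**Step 3. The two gaps together.** The illustration uses simulated data with every input assumed: two parallel arms of 20,000, baseline uniform on 14 to 24, mean ESS falls of 2 (control) and 4 (active), SD 4, and logistic regression on treatment and baseline. It is not the SAP's crossover mixed model; it serves only to show direction.

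| Status rule | Level modelled | Tabulated status rate, control / active | Odds ratio, active vs control |
|---|---|---|---|
| Intended | responder | 26.5% / 44.5% | 2.25 |
| Intended | other level | 26.5% / 44.5% | 0.44 |
| Literal | status = 1 | 75.7% / 58.0% | 0.44 |
| Literal | status = 0 | 75.7% / 58.0% | 2.28 |

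Either gap alone reverses the odds ratio. Together they cancel in the model, with 2.28 against 2.25 because of the ties, while the frequency table stays inverted. |z| is 37.4 in both intended-rule rows and 37.2 in both literal-rule rows.

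**Step 4. Fallback test.** The exact McNemar test in SAP 5.6.3 is symmetric in the discordant cells. With assumed counts of 18 and 8, p = 0.076, and swapping the cells gives the same value.

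**The case against.** The strongest reply is that nobody would be misled. The intended direction is stated in SAP 2.2.3 and twice in the protocol, section 7 of the SAP declares no change, and a change of at least -25% is readily heard as a fall of at least a quarter. The code is a template with placeholders. A coding that sorts responders first could leave the model the right way round, and the table shells attached to the SAP, which are not in the text available here, may label the modelled level. An odds ratio reversed by the event level alone would also visibly contradict the frequency tables the SAP requires alongside it.

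Much of this stands. The intent is clear, so this is a sentence to correct and not a redefined endpoint. The event-level part is conditional, because neither the coding nor the default level is given in the documents.

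A reader might infer that the status and the model both run the wrong way, so that the responder result is fully reversed. The documents do not support that. Under the literal rule with the lower level modelled, the two inversions cancel in the odds ratio. A reader might also infer that significance is at risk from the event level; it is not, since two-sided p-values and the McNemar result do not depend on it.

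What the reply does not remove is that the operative rule in 5.6.3 is wrong under the SAP's own formula, and that the SAP text leaves the direction of two sets of model tables unspecified.

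**Conclusion.** The point holds as a minor drafting defect in two parts.

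- **Responder rule (5.6.3 only).** This part is certain from the text. Taken literally, the rule selects the complement of the stated endpoint, apart from ties at exactly -25%, and would invert the responder frequency tables.
- **Event level (5.6.3 and 5.6.4).** The omission is certain; its effect is conditional. If the status is coded 0/1 and the lower level is modelled, the log-odds, odds ratios and back-transformed probabilities describe non-response, or presence of residual somnolence. Odds ratios become reciprocals; inference does not change.

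If both occurred, the responder model table would be right apart from ties and would disagree with its own frequency table. In 5.6.4 only the event-level part applies, so no such cancellation is possible.

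Only secondary endpoints are touched, in a trial the SAP calls exploratory. The key efficacy analysis of ESS change in 5.6.1 is unaffected. The rates and odds ratios above are illustrations, not trial values.

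**What to change.** - In SAP 5.6.3, define a responder as a subject with relative change ≤ -25% (that is, at least 25% improvement).
- State the coding: 1 = responder in 5.6.3, and 1 = ESS < 11 in 5.6.4.
- Name that level as the event, for example `<Responder Status>(EVENT='1')`, in every GLIMMIX MODEL statement used for 5.6.3 and 5.6.4, including the first-period models.

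The cost is a few words of text and one option per MODEL statement. No new data, analysis or sample size is needed.

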#### **5.6.4 Absence of Residual Somnolence**

Residual somnolence is defined as an ESS score of 11 or more at the end of a treatment period. The rate of subjects with an absence of residual somnolence (i.e. ESS score < 11) at the end of each treatment period will be analysed using statistical methods described in Section 5.6.3.

In the case that a statistically significant (p-value < 0.05) treatment by period interaction is found in the model-based analysis of residual somnolence, an additional analysis will be performed using only data collected during the first treatment period. The statistical methods will be adjusted as described in Section 5.6.3.

The following tables will be presented:

Table 15.3.5.1.1.S Summary of Absence of Residual Somnolence – Full Analysis

Table 15.3.5.1.2.S Summary of Absence of Residual Somnolence – Per Protocol

Table 15.3.5.2.1.T Summary of Absence of Residual Somnolence – Full Analysis

Table 15.3.5.2.2.T Summary of Absence of Residual Somnolence – Per Protocol

Absence of residual somnolence at each post-baseline visit will be summarised using default frequency tabulations. Percentage will be based on number of subjects with data available at each timepoint.

Table 15.3.6.1.1 Analysis of Absence of Residual Somnolence – Full Analysis

Table 15.3.6.1.2 Analysis of Absence of Residual Somnolence – Per Protocol

Table 15.3.6.2.1 Analysis of Absence of Residual Somnolence (First Period) – Full Analysis

Table 15.3.6.2.2 Analysis of Absence of Residual Somnolence (First Period) – Per Protocol

Estimates of each modelled effect will be displayed with standard errors, t-values and p-value. Log-odds contrast estimates will be displayed for the difference between each pair of treatments.

#### **5.6.5 Psychomotor Vigilance Test (PVT)**

On visits VR, V1B, V1C, V2B, V2C, and V3B/EDV subjects will undergo 3-minute Psychomotor Vigilance Task evaluations. PVT will be performed up to four times during each visit: at 10:00 h, 12:00 h, 14:00 h, and 16:00 h ( $\pm 15$  minutes each) by default. If the default PVT schedule is too burdensome for a particular subject, it may be individually adapted to at least 3 assessments with a time window of at least 1 hour between each PVT assessment. The actual time of each PVT assessment will be collected in the eCRF.

The following PVT variables will be collected at every visit and timepoint:

- Mean response time (ms)
- Number of lapses
- Number of total errors

A failure to react or any reaction exceeding 500 ms is considered a lapse. A reaction without stimulus or under 100 ms is considered a false start. Lapses and false starts are counted towards total errors.

For each PVT variable, the mean value during a visit will be used for analysis.

The PVT mean response time will be analysed using a mixed linear regression model as described in Section 5.6.1.

In the case that a statistically significant ( $p$ -value  $< 0.05$ ) treatment by period interaction is found in the analysis of the PVT mean response time, an additional analysis will be performed using only data collected during the first treatment period. The statistical model will be adjusted as described in Section 5.6.1.

The following tables, listing, and figures will be presented:

Table 15.3.7.1.1.S Summary of PVT Mean Response Time – Full Analysis

Table 15.3.7.1.2.S Summary of PVT Mean Response Time – Per Protocol

Table 15.3.7.2.1.T Summary of PVT Mean Response Time – Full Analysis

Table 15.3.7.2.2.T Summary of PVT Mean Response Time – Per Protocol

PVT mean response time will be summarised using default summary statistics at each visit. The change from baseline will be summarised at each post-baseline visit.

Table 15.3.8.1.1.S Summary of PVT Errors – Full Analysis

Table 15.3.8.1.2.S Summary of PVT Errors – Per Protocol

Table 15.3.8.2.1.T Summary of PVT Errors – Full Analysis

Table 15.3.8.2.2.T Summary of PVT Errors – Per Protocol

The number of lapses and number of total errors during PVT evaluation will be summarised using default summary statistics at each visit. The change from baseline will be summarised at each post-baseline visit.

Table 15.3.9.1.1 Analysis of PVT Mean Response Time – Full Analysis

Table 15.3.9.1.2 Analysis of PVT Mean Response Time – Per Protocol

Table 15.3.9.2.1 Analysis of PVT Mean Response Time (First Period) – Full Analysis

Table 15.3.9.2.2 Analysis of PVT Mean Response Time (First Period) – Per Protocol

Estimates of each modelled effect will be displayed with standard errors,  $t$ -values and  $p$ -values. Contrast estimates will be displayed for the difference between each pair of treatments.

Figure 15.3.3.1.S Subject-Level PVT Performance Change from Baseline – Full Analysis

Figure 15.3.3.2.S Subject-Level PVT Performance Change from Baseline – Per Protocol

PVT mean response time change from baseline at the end of every treatment period will be displayed for each subject stratified by treatment sequence.

Figure 15.3.4.1.T Mean PVT Performance Change from Baseline by Period – Full Analysis

Figure 15.3.4.2.T Mean PVT Performance Change from Baseline by Period – Per Protocol

The mean and standard deviation of PVT mean response time change from baseline pooled by treatment at the end of every treatment period will be displayed using a scatter plot with error bars.

Listing 16.2.9.2 Psychomotor Vigilance Test – Enrolled

PVT variable data will be listed for each subject in the enrolled analysis set.

## 5.6.6 Montreal Cognitive Assessment (MoCA)

The Montreal Cognitive Assessment (MoCA) is a brief screening instrument to detect mild cognitive impairment. The MoCA assesses multiple cognitive domains including attention, concentration, executive functions, memory, language, visuospatial skills, abstraction, calculation and orientation. Subjects will complete the MoCA during the screening and washout visits VS1, VR, V1C, and V2C, and on end-of-treatment visits V1B, V2B, and V3B/EDV.

To decrease possible learning effects, the three (equivalent) versions 7.1, 7.2, and 7.3 will be used in alternation. MoCA scores range between 0 and 30. A score of 26 or over is considered to be normal.

For subjects with an education of 12 years or fewer, the MoCA score will be increased by 1. MoCA scores of 30 will not be increased.

MoCA scores will be analysed using a mixed linear regression model as described in Section 5.6.1.

In the case that a statistically significant ( $p$ -value  $< 0.05$ ) treatment by period interaction is found in the analysis of the MoCA score, an additional analysis will be performed using only data collected during the first treatment period. The statistical model will be adjusted as described in Section 5.6.1.

The following tables and listing will be presented:

Table 15.3.10.1.1.S Summary of Montreal Cognitive Assessment Scores – Full Analysis

Table 15.3.10.1.2.S Summary of Montreal Cognitive Assessment Scores – Per Protocol

Table 15.3.10.2.1.T Summary of Montreal Cognitive Assessment Scores – Full Analysis

Table 15.3.10.2.2.T Summary of Montreal Cognitive Assessment Scores – Per Protocol

The Montreal Cognitive Assessment score will be summarised using default summary statistics at each visit. The change from baseline will be summarised at each post-baseline visit.

Table 15.3.11.1.1 Analysis of Montreal Cognitive Assessment Scores – Full Analysis

Table 15.3.11.1.2 Analysis of Montreal Cognitive Assessment Scores – Per Protocol

Table 15.3.11.2.1 Analysis of Montreal Cognitive Assessment Scores (First Period) – Full Analysis

Table 15.3.11.2.2 Analysis of Montreal Cognitive Assessment Scores (First Period) – Per Protocol

Estimates of each modelled effect will be displayed with standard errors,  $t$ -values and  $p$ -values. Contrast estimates will be displayed for the difference between each pair of treatments.

Listing 16.2.9.3 Montreal Cognitive Assessment– Enrolled

